11. DATA MANAGEMENT

11.1. Access to Data

Direct access will be granted to authorised representatives from the Sponsor and host institution for monitoring and/or audit of the study to ensure compliance with regulations.

11.2. Data Recording and Record Keeping

Data will be collected prospectively on data collection sheets completed by the anaesthetist / investigator during anaesthesia. Each site will manage their own data set and the data will be pooled at the end of the recruitment phase across all sites. Data will be sent from sites to the lead study team only at the end of the data collection.

Consent form and initial data collection forms will be filed in the master folder and kept locked in the dedicated research locker in the department.

Each site will assign a study ID for each participant and a record of these IDs will be kept in the site file. Only anonymised data will be sent from each trust to the main study team. No personal data will be sent to the coordinating centre.

Management of data at sites

At each participating site participants will be assigned a trial ID at the moment of enrolment. The log of trial IDs and patient data will be kept in the site file in a locked cupboard in the anaesthetic department in each site. It will be separate to the CRF. The PI at each site will have access to this log.

The trial ID will be noted on the CRF and the consent form.

Data will be recorded by hand on the CRF by the investigator and later will be transcribed on a study database / excel spreadsheet kept on the Trust servers. The CRF will be identifiable by study ID only.

The hard copies of the consent forms and CRF will be kept locally, but separately, in the anaesthetic departments in secure locked filing cabinets.

Electronic data will be kept on a password protected database/excel spreadsheet stored on NHS servers on the hospital intranet of each site (this means it is backed up).

Telephone numbers will be accessed from hospital records with the consent of the participant. If the investigator chooses to record the telephone number of patient, this will be recorded on a separate electronic file, not on the enrolment log, and the file will be destroyed within three months of the study ending. The PI on each site will have access to the research files. Personal data be kept for 3 months and study data be kept for 5 years.

The only data that will be shared with the lead study team will be the data spreadsheet that will only have study IDs and no identifiable data. It will be sent electronically and the password will be sent separately to the spreadsheet.

Data from the research sites will be shared with the lead site only by using secure NHS email accounts.

Management of data by lead study team

The lead study team will receive the anonymised data spreadsheet, on which information will be recorded with study ID only.

All the information will be collated and stored, anonymously, entered onto a central database on OUH trust servers, with each participant identifiable by the study ID.

Study the data be kept for 5 years.

12. QUALITY ASSURANCE PROCEDURES

The study may be monitored, or audited in accordance with the current approved protocol, GCP, relevant regulations and standard operating procedures.

13. ETHICAL AND REGULATORY CONSIDERATIONS

13.1. Declaration of Helsinki

The Investigator will ensure that this study is conducted in accordance with the principles of the Declaration of Helsinki.

13.2. Guidelines for Good Clinical Practice

The Investigator will ensure that this study is conducted in accordance with relevant regulations and with Good Clinical Practice.

13.3. Approvals

The protocol, informed consent form, participant information sheet and any proposed advertising material will be submitted to an appropriate Research Ethics Committee (REC), and HRA for written approval.

The Investigator will submit and, where necessary, obtain approval from the above parties for all substantial amendments to the original approved documents.

13.4. Reporting

The CI shall submit once a year throughout the study, or on request, an Annual Progress report to the REC Committee, HRA (where required) host organisation and Sponsor. In addition, an End of Study notification and final report will be submitted to the same parties.

13.5. Participant Confidentiality

No participant identifiable data will be published.

The study staff will ensure that the participants' anonymity is maintained. The participants will be identified only by a participant ID number on all study documents and any electronic database, with the exception of the CRF, where participant initials may be added. All documents will be stored securely and only accessible by study staff and authorised personnel. The study will comply with the Data Protection Act, which requires data to be anonymised as soon as it is practical to do so.

13.6. Expenses and Benefits

No payment will be made to participants.

13.7. Other Ethical Considerations

There are no other ethical issues involved in this study.

14. FINANCE AND INSURANCE**14.1. Funding**

The study is funded to the requested sum of £56,400, £20,000 of which would be paid immediately for consumables and the rest to be held as a contingency if needed, and there is no time limit although DAS reserves the right to withdraw the funds from January 2022. Costs of devices are covered by a grant from the Difficult Airway Society (DAS) to the University of Oxford for the sum of £15,400. The rest of the grant money is for a PhD through DAS and has no bearing with the funds available for the study. We are awaiting an invoice from DAS that soon should be raised and we will (via the university) pay this sum over to them, soon after which the devices will arrive.

Each research site will obtain the devices directly from the central store area. The orders will be placed with the company Teleflex, and on the orders will be specified which site to send the devices to. Once the order is placed the company will ship them as required.

Each researcher is a consultant with an NHS contract. This consists of Direct Care Programmed Activities (DCC) and Supporting Professional Activity (SPA). The latter is, within the contract, up to 10 hours per week, and is assigned to activities including research and quality improvement. If a consultant does not deliver on these goals or use that paid time for these activities s/he is in breach of contract. Moreover, if they seek or take additional payment for these activities then they are being paid twice for the same work which is illegal. Moreover, the use of SPA time (up to 10 hours/wk) in any given year is specified at Appraisal which is a mandatory and directional meeting to assign goals for the coming year. Therefore, this project is explicitly factored in to the fully funded development goals.

A study coordinator will be put in place covered by funding from the Difficult Airway society.

14.2. Insurance

NHS bodies are legally liable for the negligent acts and omissions of their employees. If you are harmed whilst taking part in a clinical research study as a result of negligence on the part of a member of the study team this liability cover would apply.

Non-negligent harm is not covered by the NHS indemnity scheme. The Oxford University Hospitals NHS Foundation Trust, therefore, cannot agree in advance to pay compensation in these circumstances.

In exceptional circumstances an ex-gratia payment may be offered.

15. PUBLICATION POLICY

The Investigators will be involved in reviewing drafts of the manuscripts, abstracts, press releases and any other publications arising from the study. Authors will acknowledge that

the study was funded by DAS. Authorship will be determined in accordance with the ICMJE guidelines and other contributors will be acknowledged.

17. APPENDIX A: STUDY FLOW CHART

SCHEDULE OF OBSERVATIONS

SAD insertion time (from picking up device until upstroke of 1 st square wave capnography trace)
SAD insertion attempts
Cuff volume to achieve 60cmH₂O cuff pressure
Leak pressure: pressure at which audible leak starts or airway pressure plateaus, with fresh gas flow set at 5L/ min
Score following parameters using 11-point NRS (0 – very difficult / inadequate, 10 – very easy / excellent) Ease of insertion Adequacy of ventilation Hands free anaesthesia or overall usefulness of device
Note airway manipulations to maintain airway: Additional Neck extension Neck flexion Chin lift Additional Jaw thrust
Note following complications during device insertion / airway maintenance / removal of device: Failure to establish airway Loss of adequate airway Soft tissue damage Dental damage Regurgitation Aspiration Laryngospasm Stridor Coughing Gagging Hiccough Desaturation
After surgery note following events: Vomiting Lip or tongue swelling Hearing changes Ear pain Sore throat Dysphagia Sore jaw Dysphonia Numbness of tongue / oropharynx Pain on speaking Neck or mouth ache

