3. BACKGROUND AND RATIONALE

Background

A supraglottic airway device (SAD) is used in the airway management of patients undergoing general anaesthesia. It has two major components, a 'mask' which forms a seal over the glottis with or without the use of an inflatable cuff, and an 'airway tube' which transmits gases during ventilation from the mask to the anaesthetic breathing system (1). After the patient is anaesthetised, the device is advanced into the mouth over the tongue into the pharynx, resting in the hypopharynx and covering the supraglottic structures. This enables relative isolation of the trachea from other structures such as the oesophagus. Although the use of

SADs is primarily to enable ventilation during general anaesthesia where endotracheal intubation is deemed unnecessary or inappropriate, they also have an important role in the management of the difficult airway either as a rescue device or as a channel to intubate the trachea via fibre optic intubation (2).

The original SAD, the laryngeal mask airway (LMA), was developed in the UK by Archie Brain and entered widespread use in 1989. Now named the LMA classic (cLMA) it was quickly adopted by the profession and revolutionised anaesthetic practice around the world. In 2010 the Royal College of Anaesthetists (RCOA) carried out the 4th National Audit Project, which analysed major complications of airway management in the UK. At this time, a SAD was in use in more than 50% of all general anaesthetics, the majority using either the cLMA or similar design (3,4).

In the years since the introduction of the cLMA numerous new SADs have been developed. Initially these shared similar characteristics with the cLMA and have been named '1st generation' devices. The use of these devices carries a low but recognised risk of complications including aspiration of gastric contents, inadequate laryngeal seal, post-operative sore throat and difficulties with device insertion (3). In an attempt to address these issues manufacturers have developed '2nd generation' SADs, which are designed to reduce the risk of aspiration and may claim features such as easier insertion, reduced trauma on insertion, superior seal pressures, and integral bite blocks (5,6). These improvements have led to true advancement in the field (7-10) and have led to calls from experts for 2nd generation device use to become a standard of care (11).

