In 2011 the Difficult Airway Society (DAS), in response to concerns from the anaesthetic community that devices used in airway management were being introduced into clinical practice with minimal trial based evidence of their benefit, formed the ADEPT (Airway Device Evaluation Project Team) working group. The group made a number of recommendations on the evaluation of airway equipment prior to purchase, published in *Anaesthesia* in 2011 (12). These were subsequently adopted by DAS as guidance to its members involved in the procurement of airway equipment. The ADEPT guidance identifies that, although such devices may be sold under the Medical Devices Directive with little evidence of efficacy and safety, they should not be bought and used unless there is a minimum standard of evidence available proving such. The minimum acceptable level of evidence according to ADEPT guidance is 3b, i.e. a single case-control or historical case-control study, with more robust evidence preferred if feasible and practical. The guidance is clear that it does not consider RCT (1b) or systematic review (1a) to be necessary for airway device evaluation where more pragmatic and less resource intensive study designs may be adequate (12).

Rationale

The LMA® Protector™ is a new single use SAD developed by Teleflex inc. It is a 2nd generation device which has a number of additional features compared to previous designs, incorporated to improve the safety of the device (13). These features are:

- Allows access to and functional separation of respiratory and digestive tracts
- Two drainage channels enabling either direct suction at the upper oesophageal sphincter or the passage of a gastric tube
- Integrated bite block

- A fixation system preventing proximal displacement
- An elongated cuff enhancing the seal at the distal end of the mask at the upper oesophageal sphincter, designed to potentially reduce risk of aspiration
- An integrated cuff pressure indicator enabling continuous monitoring of cuff pressure and optimisation (Cuff Pilot™ Technology)
- Enables passage of tracheal tubes up size 7.5mm internal diameter

The device is an evolution on the design of previous 2nd generation SADs developed by Intavent Orthofix and now owned by Teleflex which are in everyday use around the world - LMA® ProSeal™, the LMA® Supreme™, and the Guardian CPV™ airways, all with good evidence of safety and efficacy (7-10).

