7.6. Subsequent Visits

First visit

During the first visit by the anaesthetist to the participant, at the anaesthetist's earliest opportunity, either in the recovery area or on the ward, the participants will be asked about the following complications, which will be graded as none, mild, moderate or severe).

- 1) Vomiting
- 2) Lip or tongue swelling
- 3) Hearing changes
- 4) Ear pain
- 5) Sore throat
- 6) Pain on swallowing
- 7) Jaw pain
- 8) Neck or mouth ache
- 9) Pain on speaking
- 10) Numbness of the tongue

Second visit (or telephone consultation)

During the second visit 24-48 hours post-operatively on the ward or via telephone the participants will be asked about the following complications, which will be graded as none, mild, moderate or severe).

- 1) Vomiting
- 2) Lip or tongue swelling
- 3) Hearing changes
- 4) Ear pain
- 5) Sore throat
- 6) Pain on swallowing
- 7) Jaw pain
- 8) Neck or mouth ache
- 9) Pain on speaking
- 10) Numbness of the tongue

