8.2. Maintenance and storage of the device

The devices are single use. They will be stored in the anaesthetic store rooms in the operating theatre suites at the John Radcliffe, Churchill, West Wing, Women's Centre, and Nuffield Orthopaedic theatres.

9. SAFETY REPORTING**9.1. Definitions****9.1.1 Adverse Event (AE):**

An AE or adverse event is:

Any untoward medical occurrence in a patient or other clinical investigation participant taking part in a trial of a medical device, which does not necessarily have to have a causal relationship with the device under investigation.

An AE can therefore be any unfavourable and unintended sign (including an abnormal laboratory finding), symptom or disease temporally associated with the use of the device, whether or not considered related to the device.

9.1.2: Adverse Device Effect (ADE)

All untoward and unintended responses to the medical device.

The phrase "responses to a medical device" means that a causal relationship between the device under investigation and an AE is at least a reasonable possibility, i.e., the relationship cannot be ruled out.

All cases judged by either the reporting medically qualified professional or the sponsor as having a reasonable suspected causal relationship to the device qualifies as a device effect. This also includes any event resulting from insufficiencies or inadequacies in the instruction for use or deployment of the device and includes any event that is a result of a user error.

9.1.3 Serious Adverse Event (SAE):

SAE is an adverse event that

- ♣ Led to death
- ♣ Led to fetal distress, fetal death or congenital abnormality or birth defect.
- ♣ Led to serious deterioration in the health of the subject that
 - Resulted in a life-threatening illness or injury

NOTE: The term "life-threatening" in the definition of "serious" refers to an event in which the participant was at risk of death at the time of the event; it does not refer to an event which hypothetically might have caused death if it were more severe.

 - Resulted in a permanent impairment of a body structure or a body function
 - Required in-patient hospitalisation or prolongation of existing hospitalisation
 - Resulted in medical or surgical intervention to prevent permanent impairment to a body structure or a body function
 - Other important medical events*

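### Aspiration is actively recorded only up to device removal; neither post-operative interview asks about respiratory symptoms or unplanned care, so later cases may be under-ascertained

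*Combined protocol and SAP*

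**What the plan says.** Section 3 puts aspiration first among the complications of first-generation devices ("The use of these devices carries a low but recognised risk of complications including aspiration of gastric contents") and describes the elongated cuff of the study device as "designed to potentially reduce risk of aspiration". Section 4 makes airway-related complications after the anaesthetic a secondary objective, to be assessed post-operatively as well as during anaesthesia.

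Data collection falls into three parts:

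- **Up to removal.** Appendix A instructs: "Note following complications during device insertion / airway maintenance / removal of device". That list includes "Regurgitation Aspiration Laryngospasm Stridor Coughing Gagging Hiccough Desaturation". The matching outcome measure in section 4 (number 4) also ends at device removal.
- **After removal.** Section 7.6 plans two contacts, the second at 24 to 48 hours, in person or by telephone. At each, "the participants will be asked about the following complications, which will be graded as none, mild, moderate or severe". The list has ten items. Section 8.1 gives a list of eight and Appendix A a list of eleven, which starts "After surgery note following events: Vomiting Lip or tongue swelling Hearing changes Ear pain Sore throat Dysphagia Sore jaw Dysphonia".
- **Adverse events.** Section 9.2 requires every adverse event that the investigator observes or the participant reports to go on the CRF, whether or not it is related to the device. Section 9.1.3 makes an event serious if it "Required in-patient hospitalisation or prolongation of existing hospitalisation". Section 9.3 requires serious events to be reported within one working day of the team becoming aware of them.

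**The concern.** Aspiration is not always recognised in theatre. It may first show as cough, breathlessness, a chest infection or an unplanned stay. The post-operative lists are confined to throat, mouth, jaw, neck, ear and voice symptoms, with vomiting on two of the three. A participant telephoned at home about these symptoms has no prompt to mention a chest problem or a readmission.

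The stake is how a low or zero count would be read. The study is meant to inform a judgement on the device's safety and its place in UK practice. It has one arm, so no comparator would reveal incomplete capture. Section 10.2 endorses quoting an upper 95% confidence limit for all results, and a reader will take such a limit for aspiration as covering the whole follow-up. If late cases are captured less completely than early ones, the limit is too optimistic.

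**Working it through.** **1. Compare the lists.**

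| Place | Period | Aspiration or regurgitation | Respiratory item | Unplanned stay, readmission or medical contact |
|---|---|---|---|---|
| Appendix A, complications list | Insertion to removal | Yes, both | Yes (e.g. laryngospasm, coughing, desaturation) | No |
| Section 4, outcome measure 4 | Insertion to removal | As pre-defined list | As pre-defined list | No |
| Section 7.6, both contacts (10 items) | Recovery or ward; 24–48 h | No (vomiting is nearest) | No | No |
| Section 8.1 (8 items) | Recovery or ward; 24–48 h later | No | No | No |
| Appendix A, post-operative list (11 items) | After surgery | No (vomiting is nearest) | No | No |
| Section 9.2, adverse events | Whole study | If observed or reported | If observed or reported | If observed or reported |

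Section 7.5 also names post-operative complications in general terms (item 13). Its closing paragraph and section 5 (item 16) narrow the post-operative enquiry to oropharyngeal sequelae, so this line does not clearly close the gap.

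**2. Reproduce the plan's own precision figures.** Section 10.3 gives upper limits of 6.54% (n = 1000) and 6.05% (n = 2000) for a 5% failure rate. The two-sided 95% Clopper-Pearson upper limit is the 0.975 quantile of Beta(x + 1, n − x).

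- x = 50, n = 1000: 6.539%
- x = 100, n = 2000: 6.048%

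Both match, so the same method is used below. The plan gives no precision figure for aspiration.

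**3. Zero observed aspirations.** With x = 0 the upper limit is 1 − 0.025^(1/n).

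- n = 1100: 1 − 0.025^(1/1100) = 0.335%
- n = 2000: 1 − 0.025^(1/2000) = 0.184%

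These limits apply to the rate of captured events. They equal limits for the true rate only if every case is captured.

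**4. Effect of incomplete capture (illustration).** Let s be the share of true cases that reach the count by any route, including section 9.2. The documents give no value for s, so the values here are assumptions. Observed rate = s × true rate, so the compatible true rate is the limit divided by s.

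| s (assumed) | n = 1100 | n = 2000 |
|---|---|---|
| 1.00 (no loss) | 0.33% | 0.18% |
| 0.75 | 0.45% | 0.25% |
| 0.50 | 0.67% | 0.37% |

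**5. How much this matters depends on the true rate, which is also not given.** The chance of seeing no case is (1 − s × p)^n.

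| True rate p (assumed) | n | s = 1 | s = 0.5 |
|---|---|---|---|
| 0.1% | 1100 | 0.33 | 0.58 |
| 0.1% | 2000 | 0.14 | 0.37 |
| 0.01% | 1100 | 0.90 | 0.95 |

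At 0.1%, halving capture makes a reassuring zero much more likely. At 0.01%, sampling error dominates and capture hardly matters.

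**The case against.** A reader might infer that late aspiration is missed by design and that the reported rate is therefore biased low. The documents do not support that. Section 9.2 requires observed and reported adverse events to be recorded whatever their cause, and an admission or prolonged stay becomes reportable once the team knows of it. The investigator is the treating anaesthetist, sees participants in recovery or on the ward, and sees those still in hospital again at 24 to 48 hours. Respiratory distress or a cancelled discharge could be noticed at those contacts without a question. Nothing says that aspirations found this way are left out of the complication rate. Section 7.6 lists topics rather than verbatim questions, and the CRF is not among the documents, so a general adverse event prompt cannot be ruled out.

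It can also be said that aspiration is not a primary outcome, that section 6.2 excludes patients at risk of regurgitation, and that the analysis is descriptive, so few events would be expected in any case.

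All of this stands, and it narrows the point. It does not remove it. Observation is largely unavailable once a participant is at home. The reporting clock in section 9.3 starts with awareness, which no listed question creates. Nor does the plan say that adverse event records do feed the complication rate.

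**Conclusion.** The point holds as a gap in active ascertainment after device removal. It falls mainly on participants discharged before the second interview; the documents do not say how many that will be. Incomplete capture can only lower the observed count, but whether it occurs, and how much, cannot be worked out from the documents.

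The firm figures are the zero-event limits of 0.33% (n = 1100) and 0.18% (n = 2000), which are conditional on full capture. The larger values at s = 0.75 and 0.50 show sensitivity to an assumed capture share; it would be wrong to read them as the true limits.

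It would also be wrong to treat aspiration as the study's headline endpoint because it is named first in the background. The primary outcomes are first-go insertion, first-go ventilation and complication-free insertion, assessed at the time of anaesthesia. They and the sample size are untouched. What is affected is the secondary description of complications after anaesthesia and the count of airway-related serious events. This is an inexpensive improvement to a secondary safety result.

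**What to change.** 1. Add two questions to both interviews, in sections 7.6 and 8.1 and in Appendix A: one on new respiratory symptoms or chest infection since surgery, and one on any unplanned overnight stay, prolonged stay, readmission or medical contact since surgery.
2. Handle a positive answer through the adverse event recording and relatedness assessment already in section 9.2, with seriousness judged under section 9.1.3.
3. State in section 10 that aspirations identified through adverse event or serious adverse event reports count in the complication rate.
4. Report aspiration seen up to device removal separately from any aspiration up to the second interview, each with its exact 95% upper limit.

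**Cost.** A protocol amendment, two CRF lines and a little more time at contacts already planned; no new visit. Cough and overnight stays are non-specific after surgery, so some positives will be unrelated. Each will need a relatedness judgement and sometimes a check of the notes, which is extra work for sites.
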